6.2.5. Biomarker Endpoints

CCI

CCI

CCI

6.2.6. Endpoints for Immunogenicity Data of PF-05082566 and Mogamulizumab

ADA/ Nab data will be listed and summarized for PF-05082566 and mogamulizumab by dose and for the entire study population. The percentage of patients with positive ADA and Nab will be summarized by dose and overall study population (eg, at baseline, post-dose, treatment-induced, treatment-boosted or anytime of the study). For patients with positive ADA, the magnitude (titer), time of onset, and duration of ADA response will also be described, if data permit. The impact of ADA/Nab on PK, safety/efficacy will also be assessed, if data permit.

6.3. Other Endpoints

6.3.1. irRECIST Endpoints

The irRECIST criteria will also be used in this study for exploratory assessments of anti-tumor activity.

The following analyses will be based on the FAS by treatment group based on Investigator assessment.

Immune-related progressive disease (irPD) needs to be confirmed by a second, consecutive assessment at least 4 weeks apart. irPD is also considered to be confirmed if the patient:

- dies within 12 weeks after the initial observation of irPD, or
- discontinues treatment due to disease progression (clinical deterioration without radiological documentation) prior to or within 12 weeks after the assessment of irPD.

Immune-related Best Overall Response (irBOR) will be derived based on reported lesion responses at different evaluation time points from the first dose of study treatment until immune-related disease progression per irRECIST, according to the following rules:

- irCR = at least two determinations of irCR at least 4 weeks apart and before irPD;
- irPR = at least two determinations of irPR or better at least 4 weeks apart and before irPD (and not qualifying for a irCR);
- irSD = at least one irSD assessment (or better) ≥ 6 weeks after the first dose of study treatment and before irPD (and not qualifying for irCR or irPR);
- irPD = at least two consecutive determinations of irPD at least 4 weeks apart;
- irNE: all other cases.

Only tumor assessments performed before the start of any further anti-cancer therapies will be considered in the assessment of irBOR.

Immune-related Objective Response (irOR) is defined as irBOR or irCR or irPR. Immune-related OR rate (irORR) is the proportion of patients with irOR in the analysis set.

Immune-related Duration of Response (irDR) is defined, for patients with an immune-related objective response, as the time from the first documentation of immune-related objective response (irCR or irPR) to the date of first documentation of irPD (which is subsequently confirmed) or death due to any cause. If a patient has not had an event (irPD or death), irDR is censored at the date of last adequate tumor assessment. The censoring rules for irDR are as described below for irPFS.

$$\text{irDR (months)} = [\text{date of event or censoring} - \text{first date of irOR} + 1]/30.4375$$

Immune-related Time to response (irTTR) is defined, for patients with an irOR, as the time from the first dose of study treatment to the first documentation of immune-related objective tumor response (irCR or irPR) which is subsequently confirmed.

$$\text{irTTR (in months)} = [\text{first date of irOR} - \text{first dose of study treatment} + 1]/30.4375$$

Immune-related Progression-Free Survival (irPFS) is defined as the time from the first dose of study treatment to the date of first irPD (which is subsequently confirmed) or death due to any cause, whichever occurs first. irPFS data will be censored on the date of the last adequate tumor assessment for patients who do not have an event (confirmed irPD or death), for patients who start a new anti-cancer therapy prior to an event or for patients with an event after 2 or more missing tumor assessments. Patients who do not have an adequate baseline tumor assessment or who do not have an adequate post-baseline tumor assessment will be censored on the first dose of study treatment unless death occurred on or before the time of the second planned tumor assessment in which case the death will be considered an event.

The censoring and event date options to be considered for the irPFS and irDR analysis are presented in Table 6.

Table 6. Outcome and Event Date for irPFS and irDR Analyses

Scenario	Date of event/censoring	Outcome
No adequate baseline assessment	first dose of study treatment	Censored ^a
irPD (subsequently confirmed) ^b or death	Date of first irPD or death	Event
- After at most one missing or inadequate post-baseline tumor assessment, OR		
- ≤ 16 weeks after the first dose of study treatment		
irPD (subsequently confirmed) ^b or death after 2 or more missing or inadequate post-baseline tumor assessments	Date of last adequate tumor assessment ^c documenting no irPD before new anti-cancer therapy is given or missed tumor assessments	Censored
Treatment discontinuation due to 'Disease progression' (clinical deterioration without radiological documentation) prior to or within 12 weeks after the assessment of first irPD	Date of first irPD	Event
New anti-cancer therapy prior to confirmed irPD	Date of last adequate tumor assessment ^c documenting no irPD before anti-cancer therapy is given or missed tumor assessments	Censored
(irPD not confirmed or no irPD) and no death	Date of last adequate tumor assessment ^c documenting no irPD before anti-cancer therapy is given or missed tumor assessments	Censored

^a However if the patient dies \leq xx weeks after the first dose of study treatment the death is an event with date on death date

^b irPD is also considered to be confirmed if the patient dies within 12 weeks after the initial documentation of irPD

^c If there are no adequate post-baseline assessments prior to irPD or death, then the time without adequate assessment should be measured from the first dose of study treatment; if the criteria were met the censoring will be on the first dose of study treatment.

The analyses for irBOR, irOR, irDR, irTTR will follow the methodology outlined for the RECIST v1.1 endpoints as follows:

- irOR will be summarized as described in [Section 6.2.2.1](#) for OR and 95% CIs will be reported.
- irBOR, irDR, irTTR and irPFS will be summarized by treatment group as described in [Sections 6.2.2.1, 6.2.2.3, 6.2.2.4, and 6.2.2.5](#) but irDR and irPFS will be analyzed using the censoring rules described in [Table 6](#).

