Appendix 3. Immune-related Response Criteria Derived from RECIST 1.1 (irRECIST)

Increasing clinical experience indicates that traditional response criteria may not be sufficient to fully characterize activity in this new era of targeted therapies and/or biologics.

This is particularly true for immunotherapeutic agents such as anti-CTLA4 and anti-PD1\anti-PDL1 which exert the antitumor activity by augmenting activation and proliferation of T cells, thus leading to tumor infiltration by T cells and tumor regression rather than direct cytotoxic effects.^{34, 35} Clinical observations of patients with advanced melanoma treated with ipilimumab, for example, suggested that conventional response assessment criteria such as RECIST and WHO criteria are not sufficient to fully characterize patterns of tumor response to immunotherapy because tumors treated with immunotherapeutic agents may show additional response patterns that are not described in these conventional criteria.^{36, 37}

Furthermore, the conventional tumor assessment criteria (RECIST and WHO criteria) have been reported as not capturing the existence of a subset of patients who have an OS similar to those who have experienced CR or PR but were flagged as PD by WHO criteria.^{36, 37}

On these grounds, a tumor assessment system has been developed that incorporates these delayed or flare-type responses into the RECIST 1.1 criteria (irRECIST).³⁸

For irRECIST, only target and new measurable lesions are taken into account. In contrast to the RECIST 1.1, the irRECIST criteria:

- Require confirmation of both progression and response by imaging at least 4 weeks from the date first documented, and
- Does not necessarily score the appearance of new lesions as progressive disease if the sum of lesion diameters of target lesions (minimum of 10 mm longest diameter per non-nodal lesion and 15 mm shortest diameter per nodal lesion, maximum of 5 target lesions, maximum of 2 per organ) and measurable new lesions does not increase by $\geq 20\%$.

The same method of assessment and the same technique should be used to characterize each identified and reported target lesion(s) at baseline and throughout the trial.

irRECIST criteria are defined as follows:

- Overall immune-related complete response (irCR): Complete disappearance of all lesions (whether measurable or not) and no new lesions. All measurable lymph nodes also must have a reduction in short axis to <10 mm.

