- Overall immune-related partial response (irPR): Sum of the diameters (longest for non-nodal lesions, shortest for nodal lesions) of target and new measurable lesions decreases $\geq 30\%$.

- Overall immune-related stable disease (irSD): Sum of the diameters (longest for non-nodal lesions, shortest for nodal lesions) of target and new measurable lesions is neither irCR, irPR, (compared to baseline) or immune-related progressive disease (irPD, compared to nadir).
- Overall immune-related progressive disease (irPD): Sum of the diameters (longest for non-nodal lesions, shortest for nodal lesions) of target and new measurable lesions increases $\geq 20\%$ (compared to nadir), confirmed by a repeat, consecutive observation at least 4 weeks from the date first documented.

New measurable lesions: Incorporated into tumor burden (ie, added to the target lesion measurements). A lymph node has to be ≥ 15 mm in short axis to be a measurable new lesion and its short axis measurement is included in the sum. Up to 2 new lesions per organ and up to 5 new lesions in total can be added to the measurements.

New non-measurable lesions: Do not define progression but preclude irCR.

Overall responses derived from changes in target, non-target, and new lesions are outlined in Table 13.

Table 13. Overall Response Derived from Changes in Target, Non-target and New Lesions

Measurable response Target and New Measurable Lesions (Tumor Burden) ^a	Non-measurable response		Overall response using irRECIST ^b
	Non-Target Lesions	New Non-Measurable Lesions	
Decrease 100%	Absent	Absent	irCR
Decrease 100%	Stable	Any	irPR
Decrease 100%	Unequivocal progression	Any	irPR
Decrease $\geq 30\%$	Absent/stable	Any	irPR
Decrease $\geq 30\%$	Unequivocal progression	Any	irPR
Decrease $< 30\%$ and increase $< 20\%$	Absent/stable	Any	irSD
Decrease $< 30\%$ and increase $< 20\%$	Unequivocal progression	Any	irSD
Increase $\geq 20\%$	Any	Any	irPD

a. Decrease assessed relative to baseline.

b. Response (irCR and irPR) and progression (irPD) must be confirmed by a second, consecutive assessment at least 4 weeks apart.

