3.2.2. Efficacy Endpoints

- Objective tumor response;

OR is defined as complete response (CR) or partial response (PR) according to RECIST v1.1 from the first dose of study treatment until the date of the first documentation of progressive disease (PD). Both CR and PR must be confirmed by repeat assessments performed no less than 4 weeks after the criteria for response are first met.

irOR is defined as immune-related CR (irCR) or immune-related PR (irPR) according to irRECIST from the first dose of study treatment until immune-related PD (irPD). Both irCR and irPR must be confirmed by repeat assessments performed no less than 4 weeks after the criteria for immune-related response are first met. Also, irPD must be confirmed by a second, consecutive assessment at least 4 weeks apart.

- Time-to-response (TTR, expansion cohorts only);

TTR is defined, for patients with an OR, as the time from the first dose of study treatment to the first documentation of objective response (CR or PR) which is subsequently confirmed.

irTTR is defined, for patients with an irOR, as the time from the first dose of study treatment to the first documentation of immune-related objective tumor response (irCR or irPR) which is subsequently confirmed.

- Duration of response (DR, expansion cohorts only);

DR is defined, for patients with OR, as the time from first documentation of objective response (CR or PR) to the date of first documentation of PD or death due to any cause.

irDR is defined, for patients with an immune-related objective response, as the time from the first documentation of immune-related objective response (irCR or irPR) to the date of first documentation of irPD (which is subsequently confirmed) or death due to any cause.

- Progression-free survival (PFS, expansion cohorts only);

PFS is defined as the time from the first dose of study treatment to the date of the first documentation of PD or death due to any cause, whichever occurs first.

irPFS is defined as the time from the first dose of study treatment to the date of first documentation of irPD (which is subsequently confirmed) or death due to any cause, whichever occurs first.

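### The SAP drops the consecutive-assessment requirement for confirming irCR and irPR that Protocol Appendix 3 (Table 13, footnote b) sets, and does not declare the change

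*SAP*

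**What the plan says.** Protocol Appendix 3 addresses confirmation in three places.

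- The introductory text says the criteria "Require confirmation of both progression and response by imaging at least 4 weeks from the date first documented". It gives an interval and does not say whether the scans must be adjacent.
- In the list of definitions, irPD calls for a repeat, consecutive observation. The irCR and irPR entries do not mention confirmation.
- Footnote b to Table 13, attached to the overall-response column, covers all three: "Response (irCR and irPR) and progression (irPD) must be confirmed by a second, consecutive assessment at least 4 weeks apart".

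The SAP separates response from progression. In 6.3.1, besides the irPR rule "irPR = at least two determinations of irPR or better at least 4 weeks apart and before irPD", it has "irCR = at least two determinations of irCR at least 4 weeks apart and before irPD", but "irPD = at least two consecutive determinations of irPD at least 4 weeks apart". SAP 3.2.2 makes the same split: "Both irCR and irPR must be confirmed by repeat assessments performed no less than 4 weeks after the criteria for immune-related response are first met", whereas "irPD must be confirmed by a second, consecutive assessment at least 4 weeks apart".

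SAP Section 1 says the plan is based on protocol amendment 1. Its change table mentions alignment of the irRECIST analysis with newer standard criteria and added censoring detail. It does not mention relaxing response confirmation.

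**The concern.** The SAP uses footnote b's own phrase for irPD and omits it for irCR and irPR in the same list. A programmer will reasonably read the omission as deliberate and code any two qualifying scans. That rule differs from footnote b whenever a non-qualifying scan falls between two qualifying ones.

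What is at stake is the reported irORR with its 95% confidence interval by treatment group and, in the expansion cohorts only, irTTR and irDR. All scheduled scans are at least 8 weeks apart apart from the visit window, so any two satisfy the 4-week gap. The number of chances to qualify therefore grows with time on study. Treatment groups are small, so a single reclassified patient is visible in the rate.

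**Working it through.** The plan gives no figure on this point, so there is none to reproduce. The check has three parts.

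**1. The two rules on example sequences.** irPR is a decrease of at least 30% from baseline; irPD is an increase of at least 20% from nadir.

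| Change from baseline at successive scans (%) | Readings | SAP 6.3.1 | Footnote b |
|---|---|---|---|
| -31, -28, -31 | irPR, irSD, irPR | responder | not confirmed |
| -31, -28, -32, -27 | irPR, irSD, irPR, irSD | responder | not confirmed |
| -31, -33, -28 | irPR, irPR, irSD | responder | responder |
| -31, -28, -28 | irPR, irSD, irSD | not confirmed | not confirmed |

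Take the second row with scans at weeks 8, 16, 24 and 32. Under the SAP the week 8 irPR is confirmed at week 24, so irTTR is about 8 weeks and irDR starts at week 8 and runs through the irSD readings. Progression does not end it: the nadir is 68% of baseline, and 1.2 × 68 = 81.6, so irPD needs a reading of about -18% or higher. For irCR, a sequence irCR, irPR, irCR is irBOR irCR under the SAP but only a confirmed irPR under footnote b. That changes the category, not irOR.

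**2. Exact difference in a simple case.** Suppose each scan independently reads irPR with probability p, ignoring irPD. The excess of any two over two adjacent is the probability of having two or more hits with none adjacent.

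- 3 scans: p²(1-p).
- 4 scans: 3p²(1-p)², because 3 of the 6 two-hit patterns are non-adjacent.
- 6 scans: 10p²(1-p)⁴ + 4p³(1-p)³.

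At p = 0.5 (true change exactly -30%) with 4 scans, any two gives 1 - 1/16 - 4/16 = 68.75% and two adjacent gives 8/16 = 50%, an excess of 18.75 points. A simulation with independent error of SD 5 percentage points gave 68.1% and 49.7%; the small gap comes from stopping at confirmed irPD.

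**3. A less favourable case for the concern.** Baseline is also measured with error, and that error is shared by all of a patient's scans. This correlates the readings and reduces the excess. Assumptions: independent error in the sum of diameters with CV 5 to 10% at baseline and at each scan, constant true burden, no attrition, 200,000 simulated patients per setting. Results at CV 8%:

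| True change | Scans | Any two (SAP) | Two consecutive | Excess (points) |
|---|---|---|---|---|
| -25% | 4 | 30.7% | 23.1% | 7.6 |
| -25% | 6 | 41.2% | 29.8% | 11.4 |
| -20% | 4 | 11.4% | 7.6% | 3.8 |
| -20% | 6 | 17.5% | 10.8% | 6.7 |

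A rerun agreed with this table to within about 0.3 points. Across CV 5 to 10%, the excess with only 3 scans is about 3 to 6 points at -25% and 0 to 3 points at -20%. At -15% it is 0 to about 4 points over 3 to 6 scans. At -30% it is about 8 to 12 points. Where every scan stays clearly beyond -30%, the two rules coincide.

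**Effect of one patient on irORR:** 100/3 = 33 points and 100/9 = 11 points at the ends of the 3 to 9 evaluable patients per dose-finding cohort, and 100/40 = 2.5 points at the full expansion total.

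**The case against.** The strongest reply is that the protocol is not uniform. Its introductory irRECIST text gives only the 4-week interval, schedule footnote 18 does the same for response, and its definition list uses *consecutive* for irPD alone. The SAP's split mirrors that list. This stands as a description, and it would be wrong to say that every part of the protocol demands consecutive confirmation of response. It does not remove the conflict. Footnote b is the specific rule for the overall response, it names irCR and irPR, and it is compatible with the more general text.

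Second, both documents allow the SAP to modify the protocol's plans, and these are not primary-endpoint analyses. That is correct, so the sponsor may choose the looser rule. What is missing is a statement that it has done so.

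Third, the looser rule has the same structure as the SAP's RECIST 1.1 best-response derivation, so a stricter irPR rule would make the two rates less comparable. This is a genuine cost of the fix.

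Fourth, the stakes are low. Efficacy is descriptive, no hypothesis is tested, and SAP 6.3.1 labels irRECIST exploratory. That also stands, although SAP 3.2.2 lists irOR under secondary efficacy endpoints and Protocol 2.2 cites Appendix 3 for objective tumour response.

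A reader might infer two further things that the documents do not support. One is that the protocol makes response harder to confirm than progression; footnote b treats them alike. The other is that irORR drives the choice of expansion tumour types. Protocol 3.1.2 refers only to emerging data from this and other studies, and the SAP's primary analysis falls 24 months after the last patient's first dose with no formal interim analysis.

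**Conclusion.** The concern holds in limited form. SAP 6.3.1 and 3.2.2 accept response sequences that footnote b does not, and the change is undeclared. The direction is certain: every responder under the consecutive rule is also one under the SAP rule, so irORR can only be equal or higher under the SAP.

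The size is not certain. It depends on how many patients sit near -30%, how many scans they have, and a measurement error that the documents do not give. Under the assumptions above, an individual patient with a true 25% decrease gains about 8 to 11 points in the probability of being called irPR over 4 to 6 scans at CV 8%. The gain is smaller with 3 scans or shallower shrinkage and nil for deep responses. These are probabilities for borderline patients, not shifts in a cohort's irORR. No size was computed for irTTR or irDR. DLT, MTD and RECIST 1.1 results are unaffected.

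**What to change.** In SAP 6.3.1 and 3.2.2, define irCR as two consecutive evaluable determinations of irCR, and irPR as two consecutive evaluable determinations of irPR or better, in each case at least 4 weeks apart and before irPD. Start irTTR and irDR at the first scan of the confirmed pair. State whether an intervening irNE is skipped, and mark this as an added convention, because footnote b does not cover it.

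If the sponsor prefers the looser rule in order to match the RECIST 1.1 derivation, the SAP should declare it as a departure from footnote b, give the reason, and also report irORR under the consecutive rule.

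The cost is a few words in two SAP sections and a change to one derivation. irORR may come out slightly lower, and irPR confirmation will be stricter than the SAP's RECIST PR rule, which should be noted wherever the two rates are shown together.

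### In SAP 6.3.1 the irBOR category irPD accepts only a second scan, so some patients whose irPD the same section treats as confirmed are tabulated as irNE

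*SAP*

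**What the plan says.** SAP 6.3.1 (irRECIST Endpoints) opens by saying when irPD counts as confirmed. The basic route is a second, consecutive assessment 4 or more weeks later. Two further routes follow: the patient "dies within 12 weeks after the initial observation of irPD", or the patient "discontinues treatment due to disease progression (clinical deterioration without radiological documentation) prior to or within 12 weeks after the assessment of irPD". The text does not limit these routes to particular endpoints.

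The irBOR rules come next. "Immune-related Best Overall Response (irBOR) will be derived based on reported lesion responses at different evaluation time points", from first dose until irPD. The irPD category is "irPD = at least two consecutive determinations of irPD at least 4 weeks apart", and the residual category is "irNE: all other cases".

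Table 6, which governs irPFS and irDR, uses the wider confirmation. Its footnote b says "irPD is also considered to be confirmed if the patient dies within 12 weeks after the initial documentation of irPD", and one of its rows makes discontinuation for clinical progression an event dated at first irPD.

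Two other places mention scan confirmation only: the irOR definition in SAP 3.2.2, and footnote b to Table 13 in protocol Appendix 3.

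**The concern.** Section 6.3.1 appears to give one definition of confirmed irPD and then a narrower one for irBOR a few lines later. irBOR is built from lesion responses at evaluation time points, so a death or a discontinuation cannot serve as the second determination. A patient confirmed only by one of those routes therefore has no irBOR category except irNE.

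The protocol makes such patients likely:

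- Section 5.4.5 makes the repeat scan mandatory only when there is no clinical deterioration.
- Section 6.3 takes patients into disease follow-up only if they have not progressed at end of treatment, and collects nothing further after progression.
- The end-of-treatment scan is skipped if one was done in the previous 8 weeks.
- SAP 6.3.1 ignores scans taken after further anti-cancer therapy has started.

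What is at stake is the split between irPD and irNE in the irBOR table. Some patients with progression that the SAP itself regards as established would be shown as not evaluable.

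**Working it through.** The plan states no figure that depends on this rule, so the check is to apply the rules to individual patients.

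**Inputs**
- Confirmation routes and irBOR categories: SAP 6.3.1. irSD needs an irSD-or-better scan at least 6 weeks after first dose and before irPD.
- Scan schedule: every 8 weeks up to 1 year (SAP 6.2.2.5), so the first on-treatment scan falls at about week 8.
- Analysis set: FAS by treatment group (SAP 6.3.1).

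**Five patients, under the current rule and with irPD in irBOR accepting any irPD that the section calls confirmed**

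| Patient | Confirmed irPD under 6.3.1? | irBOR as written | irBOR aligned |
|---|---|---|---|
| A: irPD week 8, irPD week 12 | Yes, by scan | irPD | irPD |
| B: irPD week 8, death week 12 | Yes, by death | irNE | irPD |
| C: irPD week 8, clinical discontinuation week 9 | Yes, by discontinuation | irNE | irPD |
| D: irPD week 8, never confirmed | No | irNE | irNE |
| E: irSD week 8, irPD week 16, death week 20 | Yes, by death | irSD | irSD |

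Only B and C change. E shows that an earlier qualifying irSD removes the problem, and A that a second irPD scan does.

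**Effect on the other irRECIST endpoints.** B and C are non-responders in the FAS denominator either way, so irORR is unchanged. They have no response, so irDR and irTTR do not apply. irPFS follows Table 6, which already uses the wider confirmation, so it is unchanged too.

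**Reporting of irNE.** SAP 6.3.1 sends irBOR to the methods of 6.2.2.1, which tabulate NE by reason. The reasons listed are inadequate baseline, no post-baseline assessment (death or other), all assessments NE, new therapy before the first assessment, SD too short, and PD too late. None fits a single irPD at week 8 without a second scan.

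**Size.** The documents give no rate. What can be computed is the shift per reclassified patient, 100/n percentage points. Protocol 3.1.9 allows 3 to 9 evaluable patients per dose-finding cohort, and up to 40 are planned for expansion:
- n = 3: 100/3 = 33.3 points
- n = 6: 100/6 = 16.7 points
- n = 9: 100/9 = 11.1 points
- n = 40: 100/40 = 2.5 points

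A count needs assumptions from outside the documents. Suppose 30% to 70% of about 70 patients (30 dose-finding plus 40 expansion) had irPD at the first scan, and 10% to 50% of those were confirmed only by death or clinical discontinuation. The range is then 70 × 0.30 × 0.10 = 2.1 to 70 × 0.70 × 0.50 = 24.5 patients, which is too wide to serve as an estimate.

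**The case against.** The strongest defence is that a scan-only irBOR is deliberate. SAP 3.2.2 and protocol Appendix 3 both ask for a second, consecutive assessment and mention no other route. irBOR is defined from lesion responses. The RECIST v1.1 BOR rules in 6.2.2.1, whose methodology irBOR follows, refuse clinical deterioration as evidence of progression. A scan-based best response beside event-based irPFS and irDR would be a coherent design. This stands as a possible intention, but the SAP never states it. Section 6.3.1 gives the wider confirmation without restriction just before the irBOR list, and no irNE reason covers the patients it would leave over. The text needs an edit under either reading.

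Two stronger readings are tempting, and the documents do not support them.

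- A reader might infer that the irBOR table contradicts the irPFS event counts. Patient B is an irPFS event through death in any case; confirmation only moves the event date from week 12 to week 8. Patient C does become an event through confirmation, but the SAP does not require best response and PFS to agree. Under RECIST v1.1 a first PD after week 12 can be NE for BOR and still a PFS event. PFS is also for expansion cohorts only (SAP 3.2.2), while irBOR covers the whole FAS.
- A reader might infer that the patients with the worst outcome disappear from the report. The RECIST v1.1 BOR table counts a single PD scan within 12 weeks of first dose as PD, unless the patient qualifies for a better category. Protocol 9.4 also lists response at each visit, progression date and death date by patient.

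**Conclusion.** The mismatch is real but minor. It affects FAS patients whose first adequate post-baseline scan is irPD, with no earlier qualifying irSD or better and no second irPD scan, who die within 12 weeks of the initial irPD or clinically discontinue within the section's limits. For them, the irBOR table understates irPD and overstates irNE, measured against the section's own definition.

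The number of such patients is unknown, and no count should be quoted as a finding. In small dose cohorts a single patient visibly shifts the percentages. No other irRECIST endpoint moves, and 6.3.1 describes these assessments as exploratory.

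The conclusion assumes that the confirmation paragraph applies to the whole of 6.3.1, which is how it reads. If the sponsor meant it for irPFS and irDR only, what remains is an unstated restriction and a missing irNE reason.

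**What to change.** Choose one of two repairs before the irBOR tables are programmed.

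1. **Use the section's own confirmation rule.** Redefine the irBOR category as irPD confirmed by any of the three routes given at the start of 6.3.1, and not qualifying for irCR, irPR or irSD. Keep the limits on each route: a second consecutive assessment at least 4 weeks later, death within 12 weeks after the initial irPD, and, for discontinuation, the full condition "discontinues treatment due to disease progression (clinical deterioration without radiological documentation) prior to or within 12 weeks after the assessment of irPD". A looser phrase such as discontinuation for progression would be wider than the rule being restored. Align the irPD confirmation sentence in SAP 3.2.2, and note there that the SAP extends the scan-only wording of protocol Appendix 3.

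2. **Keep irBOR scan-only.** State that irBOR uses scan confirmation while irPFS and irDR use the wider rule, and add an irNE reason for irPD without a confirmatory scan so that these patients are shown separately. That reason would also be useful under the first repair, for patients like D.

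Either repair costs a few lines of SAP text and a small change to the irBOR derivation. No new data are needed, because death and discontinuation for progression are already used in Table 6.
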